5.2. Exclusion Criteria

Participants are excluded from the study if any of the following criteria apply:

Medical Conditions:

1. Evidence or history of clinically significant hematological, renal, endocrine, pulmonary, gastrointestinal, cardiovascular, hepatic, psychiatric, neurological, or allergic disease (including drug allergies, but excluding untreated, asymptomatic, seasonal allergies at the time of dosing).
 - Any condition possibly affecting drug absorption (eg, gastrectomy, cholecystectomy).

- History of HIV infection, hepatitis B, or hepatitis C; positive testing for HIV, HBsAg, HBcAb, or HCVAb. Hepatitis B vaccination is allowed.
- Hypersensitivity to any component of the formulations

2. Other medical or psychiatric condition including recent (within the past year) or active suicidal ideation/behavior or laboratory abnormality or other conditions or situations related to COVID-19 pandemic (eg, Contact with positive case, residence, or travel to an area with high incidence) that may increase the risk of study participation or, in the investigator's judgment, make the participant inappropriate for the study.

Prior/Concomitant Therapy:

3. Use of prescription or nonprescription drugs, dietary and herbal supplements within 7 days or 5 half-lives (whichever is longer) prior to the first dose of study intervention. (Refer to [Section 6.9](#) Prior and Concomitant Therapy for additional details).
4. Current use of any prohibited concomitant medication(s) or participant unwilling/unable to use a permitted concomitant medication(s). Refer to [Section 6.9](#) Prior and Concomitant Therapy.

Prior/Concurrent Clinical Study Experience:

5. Previous administration with an investigational product (drug or vaccine) within 30 days (or as determined by the local requirement) or 5 half-lives preceding the first dose of study intervention used in this study (whichever is longer).

Diagnostic Assessments:

6. A positive urine drug test.
7. Screening seated BP ≥ 140 mm Hg (systolic) or ≥ 90 mm Hg (diastolic), following at least 5 minutes of seated rest. If BP is ≥ 140 mm Hg (systolic) or ≥ 90 mm Hg (diastolic), the BP should be repeated 2 more times and the average of the 3 BP values should be used to determine the participant's eligibility.
8. Standard 12-lead ECG that demonstrates clinically relevant abnormalities that may affect participant safety or interpretation of study results (eg, QTcF >450 ms, complete LBBB, signs of an acute or indeterminate- age myocardial infarction, ST-T interval changes suggestive of myocardial ischemia, second- or third- degree AV block, or serious bradyarrhythmias or tachyarrhythmias). If the uncorrected QT interval is >450 ms, this interval should be rate-corrected using the Fridericia method only and the resulting QTcF should be used for decision making and reporting. If QTcF exceeds 450 ms, or QRS exceeds 120 ms, the ECG should be repeated twice and the average of the 3 QTcF or QRS values used to determine the participant's

eligibility. Computer-interpreted ECGs should be overread by a physician experienced in reading ECGs before excluding a participant.

9. Participants with **ANY** of the following abnormalities in clinical laboratory tests at screening, as assessed by the study-specific laboratory and confirmed by a single repeat test, if deemed necessary:

- AST **or** ALT level $\geq 1.5 \times$ ULN;
- Total bilirubin level $\geq 1.5 \times$ ULN; participants with a history of Gilbert's syndrome may have direct bilirubin measured and would be eligible for this study provided the direct bilirubin level is \leq ULN.

Other Exclusion Criteria:

10. History of alcohol abuse or binge drinking and/or any other illicit drug use or dependence within 6 months of Screening. Binge drinking is defined as a pattern of 5 (male) and 4 (female) or more alcoholic drinks in about 2 hours. As a general rule, alcohol intake should not exceed 14 units per week (1 unit = 8 ounces (240 mL) beer, 1 ounce (30 mL) of 40% spirit, or 3 ounces (90 mL) of wine).
11. Blood donation (excluding plasma donations) of approximately 1 pint (500 mL) or more within 60 days prior to dosing.
12. History of sensitivity to heparin or heparin-induced thrombocytopenia.
13. Unwilling or unable to comply with the criteria in the Lifestyle Considerations section of this protocol.
14. Investigator site staff directly involved in the conduct of the study and their family members, site staff otherwise supervised by the investigator, and sponsor and sponsor delegate employees directly involved in the conduct of the study and their family members.
15. Use of tobacco or nicotine-containing products in excess of the equivalent of 5 cigarettes per day.

5.3. Lifestyle Considerations

The following guidelines are provided:

5.3.1. Meals and Dietary Restrictions

- Participants must abstain from all food and drink (except water) at least 4 hours prior to any safety laboratory evaluations and 10 hours prior to the collection of the predose PK sample.
- Water is permitted until 1 hour prior to study intervention administration.

- Water may be consumed without restriction beginning 1 hour after dosing. Noncaffeinated drinks (except grapefruit or grapefruit-related citrus fruit juices—see below) may be consumed with meals and the evening snack.
- Lunch will be provided approximately 4 hours after dosing.
- Dinner will be provided approximately 9 to 10 hours after dosing.
- An evening snack may be permitted.
- Participants will refrain from consuming red wine, grapefruit, or grapefruit-related citrus fruits (eg, Seville oranges, pomelos, fruit juices) from 7 days prior to the first dose of study intervention until collection of the final PK blood sample.
- While participants are confined, their total daily nutritional composition should be approximately 55% carbohydrate, 30% fat, and 15% protein. The daily caloric intake per participant should not exceed approximately 3200 kcal.

5.3.2. Caffeine, Alcohol, and Tobacco

- Participants will abstain from caffeine-containing products for 24 hours prior to the start of dosing until collection of the final PK sample of each study period.
- Participants will abstain from alcohol for 24 hours prior (or as specified above for red wine) to admission to the CRU and continue abstaining from alcohol until collection of the final PK sample of each study period. Participants may undergo an alcohol breath test or blood alcohol test at the discretion of the investigator.
- Participants will abstain from the use of tobacco- or nicotine-containing products for 24 hours prior to dosing and during confinement in the CRU.

5.3.3. Activity

- Participants will abstain from strenuous exercise (eg, heavy lifting, weight training, calisthenics, aerobics) for at least 48 hours prior to each blood collection for clinical laboratory tests. Walking at a normal pace will be permitted;
- In order to standardize the conditions on PK sampling days, participants will be required to refrain from lying down (except when required for BP, pulse rate, and ECG measurements), eating, and drinking beverages other than water during the first 4 hours after dosing;

5.4. Screen Failures

Screen failures are defined as participants who consent to participate in the clinical study but are not subsequently enrolled in the study. Screen failure data are collected and remain as source and are not reported on the CRF.

Individuals who do not meet the criteria for participation in this study (screen failure) may be rescreened.

6. STUDY INTERVENTION(S) AND CONCOMITANT THERAPY

Study interventions are all prespecified investigational and medical devices, and other interventions (eg, surgical and behavioral) intended to be administered to the study participants during the study conduct.

For the purposes of this protocol, study intervention refers to both the variant and proposed commercial 12.2 mg tafamidis free acid tablet formulations.

6.1. Study Intervention(s) Administered

Study Intervention(s)		
Intervention Name	Variant tafamidis free acid tablet	Proposed commercial tafamidis free acid tablet
Arm Name (group of participants receiving a specific treatment or no treatment)	Treatment A	Treatment B
Type	Drug	Drug
Dose Formulation	Tablets	Tablets
Unit Dose Strength(s)	12.2 mg	12.2 mg
Dosage Level(s)	1 x tablet	1 x tablet
Route of Administration	Oral	Oral
Use	Experimental	Experimental
IMP or NIMP/AxMP	IMP	IMP
Sourcing	Provided centrally by the sponsor	Provided centrally by the sponsor
Packaging and Labeling	Study intervention will be supplied to the CRU in bulk along with individual dosing containers for unit dosing.	Study intervention will be supplied to the CRU in bulk along with individual dosing containers for unit dosing.
Current/Former Name(s) or Alias(es)	PF-06291826	PF-06291826
Description	DP-004562: tafamidis 12.2 mg Round Debossed Yellow Film Coated Tablet (4% CL-SF)	DP-004196: tafamidis 12.2 mg Round Debossed Yellow Film Coated Tablet (8% CL-SF)

PFIZER CONFIDENTIAL

Study Arm(s)		
Arm Title	Treatment A	Treatment B
Arm Type	Test	Reference
Arm Description	Participants will receive a single variant 12.2 mg tafamidis free acid tablet, fasted	Participants will receive a single proposed commercial 12.2 mg tafamidis free acid tablet, fasted
Associated Intervention Labels	Variant tafamidis 12.2 mg tablets	Proposed commercial tafamidis 12.2 mg tablets

Study interventions will be supplied by Pfizer as variant and proposed commercial tafamidis 12.2 mg tablets.

6.1.1. Administration

On Day 1 of each period each participant will receive either one variant (Treatment A, Test) or proposed commercial (Treatment B, Reference) tafamidis 12.2 mg tablet under fasting conditions.

Following an overnight fast of at least 10 hours, participants will receive study intervention at approximately 0800 hours (plus or minus 2 hours). Investigator site personnel will administer study intervention during each period with ambient temperature water to a total volume of approximately 240 mL. Participants will swallow the study intervention whole, and will not manipulate or chew the study intervention prior to swallowing.

In order to standardize the conditions on PK sampling days, all participants will be required to refrain from lying down (except when required for BP, pulse rate, and ECG measurements), eating, and drinking beverages other than water during the first 4 hours after dosing.

6.2. Preparation, Handling, Storage, and Accountability

1. The investigator or designee must confirm that appropriate conditions (eg, temperature) have been maintained during transit for all study interventions received and any discrepancies are reported and resolved before use of the study intervention.
2. Only participants enrolled in the study may receive study intervention and only authorized site staff may supply, prepare, and/or administer study intervention.
3. All study interventions must be stored in a secure, environmentally controlled, and monitored (manual or automated recording) area in accordance with the labeled storage conditions with access limited to the investigator and authorized site staff. At a minimum, daily minimum and maximum temperatures for all site storage locations must be documented and available upon request. Data for nonworking days must

indicate the minimum and maximum temperatures since previously documented upon return to business.

4. Any excursions from the study intervention label storage conditions should be reported to Pfizer upon discovery along with actions taken. The site should actively pursue options for returning the study intervention to the labeled storage conditions, as soon as possible. Once an excursion is identified, the study intervention must be quarantined and not used until Pfizer provides permission to use the study intervention. Specific details regarding the excursion definition and information to report for each excursion will be provided to the site in the PCRU local/site procedures.
5. Any storage conditions stated in the SRSD will be superseded by the storage conditions stated on the label.
6. Study interventions should be stored in their original containers.
7. The investigator, institution, head of the medical institution (where applicable), or authorized site staff is responsible for study intervention accountability, reconciliation, and record maintenance (ie, receipt, reconciliation, and final disposition records), such as the IPAL or sponsor-approved equivalent. All study interventions will be accounted for using a study intervention accountability form/record.
8. Further guidance and information for the final disposition of unused study interventions are provided in the PCRU local/Site procedures. All destruction must be adequately documented. If destruction is authorized to take place at the investigator site, the investigator must ensure that the materials are destroyed in compliance with applicable environmental regulations, institutional policy, and any special instructions provided by Pfizer.

Upon identification of a product complaint, notify the sponsor within 1 business day of discovery.

6.2.1. Preparation and Dispensing

Within this protocol, preparation refers to the investigator site activities performed to make the study intervention ready for administration or dispensing to the participant by qualified staff. Dispensing is defined as the provision of study intervention, concomitant treatments, and accompanying information by qualified staff member(s) to a healthcare provider, participant, in accordance with this protocol. Local health authority regulations or investigator site guidelines may use alternative terms for these activities.

Tablets will be prepared at the CRU in the individual dosing containers by 2 operators, 1 of whom is an appropriately qualified and experienced member of the study staff (eg, physician, nurse, physician's assistant, nurse practitioner, pharmacy assistant/technician, or pharmacist).

The tablets will be provided in unit dose containers and labeled in accordance with Pfizer regulations and the clinical site's labeling requirements.

6.3. Assignment to Study Intervention

The investigator will assign participant numbers to the participants as they are screened for the study. Pfizer will provide a randomization schedule to the investigator and, in accordance with the randomization numbers, the participant will receive the study treatment regimen assigned to the corresponding randomization number.

The investigator's knowledge of the treatment should not influence the decision to enroll a particular participant or affect the order in which participants are enrolled.

6.4. Blinding

This is an open-label study.

6.4.1. Blinding of Participants

Participants will be unblinded to their assigned study intervention.

6.4.2. Blinding of Site Personnel

Investigators and other site staff will be unblinded to participants' assigned study intervention.

6.4.3. Blinding of the Sponsor

Sponsor staff will be unblinded to participants' assigned study intervention.

6.5. Study Intervention Compliance

Participants will receive study intervention directly from the investigator or designee, under medical supervision. The date and time of each dose administered in the clinic will be recorded in the source documents and recorded in the CRF. The dose of study intervention and study participant identification will be confirmed at the time of dosing by a member of the study site staff other than the person administering the study intervention. Study site personnel will examine each participant's mouth to ensure that the study intervention was ingested.

6.6. Dose Modification

As this is a single-dose study, no dose modification is permitted.

6.7. Continued Access to Study Intervention After the End of the Study

No study intervention will be provided to participants at the end of their study participation.

6.8. Treatment of Overdose

For this study, any dose of PF-06291826 greater than 12.2 mg tafamidis free acid within a 24-hour time period will be considered an overdose.

There is no specific treatment for an overdose.

In the event of an overdose, the investigator should:

1. Contact the study medical monitor within 24 hours.
2. Closely monitor the participant for any AEs/SAEs and laboratory abnormalities as medically appropriate and at least until the next scheduled follow-up.
3. Document the quantity of the excess dose as well as the duration of the overdose in the CRF.
4. Overdose is reportable to Pfizer Safety **only when associated with an SAE**.
5. Obtain a blood sample for PK analysis within 1 day from the date of the last dose of study intervention if requested by the study medical monitor (determined on a case-by-case basis).

6.9. Prior and Concomitant Therapy

Use of prescription or nonprescription drugs and dietary and herbal supplements are prohibited within 7 days or 5 half-lives (whichever is longer) prior to the first dose of study intervention. Limited use of nonprescription medications that are not believed to affect participant safety or the overall results of the study may be permitted on a case-by-case basis following approval by the sponsor. Acetaminophen/paracetamol may be used at doses of ≤ 1 g/day.

Females taking hormone replacement therapy may be eligible to participate in this study if they are willing to discontinue therapy at least 28 days prior to the first dose of study treatment and remain off hormonal therapy for the duration of the study.

All concomitant treatments taken during the study must be recorded with indication, daily dose, and start and stop dates of administration. All participants will be questioned about concomitant treatment at each clinic visit.

Treatments taken within 28 days before the first dose of study intervention will be documented as a prior treatment. Treatments taken after the first dose of study intervention will be documented as concomitant treatments.

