10.9. Appendix 9: Prohibited Concomitant Medications That May Result in DDI

Not applicable to this study.

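### Does the plan leave interacting medicines unrestricted between the two periods, because the drug ban in Section 6.9 is written only up to the first dose?

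*Protocol*

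**What the plan says.** Protocol Section 6.9 states that prescription drugs, nonprescription drugs and supplements "are prohibited within 7 days or 5 half-lives (whichever is longer) prior to the first dose of study intervention". Exclusion 3 in Section 5.2 uses the same window: "within 7 days or 5 half-lives (whichever is longer) prior to the first dose of study intervention". Neither says when the restriction ends once dosing has begun.

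Section 6.9 then adds three things that are not confined to the time before dosing:

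- "Limited use of nonprescription medications that are not believed to affect participant safety or the overall results of the study may be permitted", case by case and with sponsor approval.
- Paracetamol is capped at 1 g/day.
- Women who have stopped hormone replacement must "remain off hormonal therapy for the duration of the study".

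It also requires on-study treatments to be recorded and asked about at each clinic visit.

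Exclusion 4 refers to Section 6.9 for prohibited medications, but that section has no list. Appendix 9 (Section 10.9), the place for medicines prohibited because of interactions, reads "Not applicable to this study". Section 5.3.1, on diet, restricts grapefruit and red wine "from 7 days prior to the first dose of study intervention until collection of the final PK blood sample".

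On the analysis side, SAP Section 5.3.1 removes a known biased PK estimate from summaries and models, with dosing error and vomiting as illustrations. SAP Section 6.1 provides for residual checks and analyses without outliers.

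**The concern.** The primary estimate is a within-participant contrast from 12 people. Anything that alters exposure in both periods largely cancels, but anything that alters Period 2 alone does not. Read literally, the express ban on drugs and supplements stops at the first dose, and the eligibility criteria are checked in Period 1 only (Schedule of Activities). A participant discharged after Period 1 could start a medicine or supplement that affects tafamidis exposure, and it would not be clear that this was a protocol deviation.

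The contrast with diet sharpens the point: grapefruit, caffeine and alcohol all have stated on-study end points (Sections 5.3.1 and 5.3.2), and drugs in general do not. If such a profile stayed in the model, it would shift the estimated ratio and inflate the residual variance.

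**Working it through.** **1. The plan's own precision figure.** Inputs from Protocol Section 9.5: N = 12, within-participant SD 0.098 for log AUC, 90% CI, 80% coverage probability. Error df = 12 − 2 = 10.

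- SE of the log ratio = 0.098 × √(2/12) = 0.0400.
- Half-width = t(0.95, 10) × SE × √(χ²(0.80, 10)/10) = 0.0725 × 1.159 = 0.0841.
- At a ratio of 100%: 100 × exp(±0.0841) = 91.94% to 108.77%, as printed.

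All 14 rows of the table, AUC and Cmax, reproduce to two decimals.

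**2. What reaches past the first dose.**

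| Place | Covers | End point |
|---|---|---|
| 6.9 and Exclusion 3 | drugs and supplements in general | none stated |
| 6.9 | nonprescription drugs, with sponsor approval | none stated |
| 6.9 | paracetamol cap | none stated |
| 6.9 | hormone therapy, in women who stopped it | whole study |
| Synopsis, Ethical Considerations | live attenuated vaccines | whole study |
| 5.3.1 | grapefruit, red wine | final PK sample |

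A case-by-case permission and a dose cap make sense only against a continuing restriction, and they sit in a section that covers concomitant as well as prior therapy. The natural reading is that nonprescription use stays restricted on study. For prescription drugs and supplements the end point is simply unstated. Sections 5.3.1 and 6.9 do not contradict each other: one governs diet and the other medication.

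**3. When an unreported medicine could enter.** Participants stay in the unit from Day −1 to Day 8 of each period, which covers all sampling from 0 to 168 hours (Tables 1 and 2). With the minimum 16-day interval, Period 2 Day 1 is Period 1 Day 17 and readmission on Day −1 is Period 1 Day 16. The outpatient gap is 16 − 8 = 8 days, or longer if the washout is extended. The Schedule of Activities collects prior and concomitant medication on Day −1 and on every study day.

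**4. Size if it happened.** The documents give no interaction size, so the changes below are assumptions. Let one participant's Period 2 log exposure change by d. The treatment estimate is half the difference between the two sequence means of the within-participant differences, with 6 participants per sequence, so it moves by d/6/2 = d/12.

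- 30% increase: ln(1.3)/12 = 0.0219, or 2.2%; 0.0219/0.0400 = 0.55 SE; 0.0219/0.0841 = 0.26 of the planned half-width.
- 50% increase: ln(1.5)/12 = 0.0338, or 3.4%; 0.84 SE.
- Halving or doubling: factor 0.944 to 1.059.
- Halving or doubling in two participants of the same sequence: factor 0.891 to 1.122.

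Residual variance in the 30% case: the expected increase is d² × (5/6)/20 = 0.0029 on 0.098² = 0.0096, about 30%, so the interval widens by √1.30 = 1.14 on the log scale.

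**5. Direction.** In sequence AB, Period 2 is Reference, so a raised exposure lowers the ratio by d/12. In sequence BA, Period 2 is Test, so it raises the ratio by d/12. If such use is equally likely in both sequences, the expected shift is zero, and the part common to both is absorbed by the period effect already in the model.

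**The case for a change.** The strongest case for a change is that an implied restriction is a weak one. The approval sentence covers only nonprescription medicines. Prescription drugs and supplements have no on-study rule, even by implication, so a site could not say with confidence what counts as a deviation. The SAP does not name an interacting medicine among its examples, and concomitant medication is otherwise only listed (SAP Section 6.4.4). Whether to drop such a profile would rest on judgement in an open-label study, possibly after the concentrations are known. With 12 participants, one affected profile is visible in the result, and the remedy would cost only a sentence.

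Part of this stands. The end point is unstated, and exclusion for an interacting medicine is possible but not prespecified.

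The rest is weaker. The SAP's illustrations of a biased estimate are offered as examples, so a recorded medicine with a known effect already falls within the rule. The medication question at readmission is asked before the Period 2 dose, so the fact of use is on record before any Period 2 concentration exists. The outlier analyses in SAP Section 6.1 must be justified in the study report. Unscreened use would also need a participant just selected as healthy to start an interacting medicine in a short outpatient window.

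The missing list is less troubling than it looks. A general ban with named permissions does not need one, and a not-applicable Appendix 9 fits that reading.

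**Conclusion.** No change to the plan follows. Section 6.9 and Exclusion 3 leave the end of the drug and supplement restriction unstated, and the opening worry is correct to that extent. It is not correct that nothing applies after the first dose, nor that recording is the only on-study requirement.

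The remaining gap is narrow: mainly the outpatient days between periods, with questioning at readmission and an open-ended exclusion rule in the SAP. The illustrative effect is 2.2% on the AUC ratio, about a quarter of the planned half-width. It rests wholly on two assumptions, one affected participant in 12 and a 30% change, neither of which the documents support or refute. Larger assumed interactions, or two participants in the same sequence, would matter more, up to a factor of 0.891 to 1.122 in the range examined, but nothing in the documents makes them likely. The absence of expected bias rests on medication use being unrelated to sequence, which is reasonable when both tablets carry the same 12.2 mg dose of the same drug.

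The study tests no hypothesis (Protocol Section 9.1, SAP Section 5.1), so no stated decision turns on a shift of this size. Which period the restriction is meant to cover is for the sponsor to say; the planned analysis does not depend on the answer.
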